2.1.3 Recruitment Strategies

Potential study candidates may be referred from other NIH clinical studies to treat liver cancer. This study is “Enrolling by invitation only”.

2.2 SCREENING EVALUATION

Patients will be screened and evaluated for ability to undergo the TAE procedure by the referring physician or primary team prior to referral to this study. All screening procedures to determine if a patient is eligible for the TAE procedure, including but not limited to imaging scans, labwork, and pre-anesthesia evaluation, will be performed, ordered, reviewed and documented in the electronic medical record (CRIS) by the referring/primary team per routine clinical care. After completion of screening evaluation procedures, the primary or referring team and an interventional radiologist or his designee will document that the patient is eligible for TAE (and thermal ablation, if applicable) and direct enrollment onto this study.

2.2.1 Research Team Screening Responsibilities

Prior to enrollment in this study, the research team will review the following and place a note in CRIS of patient's eligibility:

- 1) H&P
- 2) Imaging – may include CT of the abdomen and pelvis, MRI of the abdomen, MRI/PET or CT/PET, and US of the abdomen.
- 3) Laboratory results

2.3 REGISTRATION PROCEDURES

Authorized staff must register an eligible candidate with NCI Central Registration Office (CRO) within 24 hours of signing consent. A registration Eligibility Checklist from the web site (<http://home.ccr.cancer.gov/intra/eligibility/welcome.htm>) must be completed and sent via encrypted email to: NCI Central Registration Office [contact].

Verification of Registration will be forwarded electronically via e-mail to the research team. A recorder is available during non-working hours.

Abbreviated Title: RFA + TACE with RO Beads

Version Date: 04/13/2018

2.4 TREATMENT ASSIGNMENT AND RANDOMIZATION/STRATIFICATION PROCEDURES

Cohorts

Number	Name	Description
1	Patients	Patients who have primary or metastatic liver cancer

Arms

Number	Name	Description
1	Experimental	Treatment of hepatic tumors using bead embolization

Randomization and Arm Assignment

[figure not shown]
Patients in cohort 1 will be directly assigned to arm 1

2.5 PRE-OPERATIVE (BASELINE) EVALUATION

- Review of history and physical exam
- Review of laboratory results

3 IMAGING STUDIES STUDY IMPLEMENTATION

3.1 STUDY DESIGN

¹as clinically indicated

*Patients may require re-treatment

3.2 PROCEDURE

Patients will be admitted to the NIH inpatient oncology ward and then brought to the interventional radiology suite where consent for both procedures and anesthesia using standard NIH consents will be obtained.

Standard transarterial embolization using LC Bead LUMI (Biocompatibles UK Ltd) Radiopaque Embolic radiopaque, biocompatible, non-resorbable, hydrogel beads typically with thermal ablation (microwave or radiofrequency) in an order appropriate to the clinical picture, will be administered in the Interventional Radiology Section under general anesthesia provided by the Clinical Center Department of Perioperative Medicine (DPM). Patients will remain primarily under the care of their primary team, typically NCI medical oncology service, or surgical oncology service.

The use of thermal ablation devices (RFA or MWA) and transarterial embolization will be according to manufacturer's instructions and the standard of care at the institution. Thermal ablation treatments will be administered according to the thermal ablation device instructions and the Standard of Care of the IR/CC/ NIH. The choice of which device to use will be at the discretion of the physician performing the procedure based on the factors particular to the patient's lesion(s). TAE will be administered with LC LUMI beads in accordance with the TAE device instructions and the Standard of Care of the IR/CC/ NIH and will be administered after an ablation treatment. Retreatment may be done at the recommendation of the physician, according to conventional standards. Multiple lesions may be treated with TAE with LC LUMI beads with or without thermal ablation.

3.2.1 Ablation and Embolization Procedure

During this clinical protocol, standard thermal ablation performed with general anesthesia, and CT and ultrasound guidance, often to include fusion guidance ("Medical GPS"). At the NIH, thermal ablation will be conducted according to the standard of care and practice guidelines that have been in effect for TAE and RFA treatment procedures at the CC since 1998.

TAE is the most common procedure used to treat HCC. The process involves cannulating tumor nourishing vessels and occluding the blood supply using materials such as beads, that can be combined with anti-neoplastic agents or not. The procedure involves arteriography of the superior mesenteric and celiac vasculature to identify a roadmap of vessels and vascular anomalies (accessory or replaced hepatic vasculature), confirm portal vein patency, and identify hepatic arterial anatomy. This is typically followed by a selective common hepatic arteriography to recognize non-target vessels supplying the pancreas, duodenum, or stomach. Relevant non-target vessels that cannot be excluded by distal catheter tip positioning may be selectively embolized to prevent unintended chemoembolization. For patients with multifocal disease or tumors that span both lobes, embolization of each lobe may be performed in two or more separate treatment sessions. The selected hepatic lobar artery (typically right or left) will be

Abbreviated Title: RFA + TACE with RO Beads

Version Date: 04/13/2018

catheterized for TAE with LC LUMI beads. An attempt will be made to exclude the cystic artery from the embolization distribution. Extrahepatic branch vessels may be prophylactically embolized at the discretion of the Principal Investigator to mitigate the risk of non-target deposition of LC LUMI beads. TAE will continue typically until near-complete flow stasis is observed in the target artery (where no non-target reflux of contrast material into more proximal branches is observed). If significant antegrade flow is observed in the target artery following procedure, additional embolization using LC LUMI beads may typically be added to reach the embolization endpoint. Visibility of the LC LUMI beads will be recorded using a 3 point scale: 0, definitely not visible; 1, probably visible; and 2, definitely visible. A CBCT scan *may* be obtained post LUMI beads injection to evaluate virtual perfusion characteristics of the beads for predictive investigations of their delivery and function.. The catheter will then typically be retracted into the common hepatic artery and completion arteriography will document the degree of target vessel flow stasis and non-target vessel patency.

Thermal ablation therapy may be administered based on the clinical evaluation of the patient and when appropriate will be done according to the manufacturer's instructions for use. After infiltration of the skin (for percutaneous approach) with a local anesthetic, the needle of the chosen system will be directed into the lesion, with image guidance and the needle is confirmed to be in the lesion by imaging. After confirming appropriate positioning, the lesion will be heated typically for 10-15 minutes, according to manufacturer's guidelines. The exposure time may be varied depending on the temperatures achieved and proximity of adjacent anatomy or other patient-specific anatomy or issues. Depending on the size of the lesion to be ablated, multiple locations of the needle as well as multiple ablation cycles will be performed in order to ideally achieve an approximately 1-cm margin of ablated tissue around the lesion or target volume. Adequacy of ablation will be followed by ultrasound throughout the procedure, when possible. Depending on the size of the lesions and the time required to complete the ablation, multiple lesions may be treated, often as staged procedures.

3.2.2 Post Ablation and Transarterial Embolization Care

During hospitalization, the patients will be admitted to the patient care unit following interventional procedures for routine post-procedure monitoring and inpatient care. Antibiotics, anti-emetics, hydration and comfort medicines will be administered based on the patient's clinical status. Laboratory study including a CBC, hepatic panel (alkaline phosphatase, bilirubin, AST and ALT), acute care (Na, K, Cl, CO₂, BUN, Cr), and Mineral panel (Mg, albumin, Phos, Ca,) will be typically obtained upon admission and daily post procedure, while in the hospital, according to standard clinical practice. Immediate imaging may occur if clinically indicated, based on the patient's clinical status and at the PI's discretion, as is standard of practice. Length of stay will be based on clinical status of the participant and the discretion of the PI

3.2.3 Follow up Procedures

Subsequent Clinical Center visits following treatment for study participants will be determined in accordance with the participants' primary medical or surgical oncology team and in collaboration with the study PI, as clinically indicated.

Imaging and laboratory assessments will be typically repeated as clinically warranted during the 12 months after initial treatment, or at least until evidence of disease remission, stabilization or recurrence or residual disease is documented. A CT scan will be obtained within 2 months post treatment to evaluate virtual perfusion characteristics of the LUMI beads.

Abbreviated Title: RFA + TACE with RO Beads

Version Date: 04/13/2018

3.2.4 Study Stopping Rules

Enrollment will be halted and the IRB notified if:

- Three or more patients with a non-laboratory grade 4 toxicity within the first 72 hours post TAE whether or not considered TAE or research-related.
- Death due to any cause within the first 72 hours post TAE.

All patients will be monitored until there is improvement or resolution of toxicity. Once the IRB, has completed their review; they must give their permission for the study to resume.

Abbreviated Title: RFA + TACE with RO Beads

Version Date: 04/13/2018

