3.4 CRITERIA FOR REMOVAL FROM PROTOCOL THERAPY AND OFF STUDY CRITERIA

3.4.1 Criteria for removal from protocol therapy

- Toxicity that prevents further imaging (e.g., renal dysfunction as serum creatinine >2.0mg/dl and precludes CT or MRI imaging)
- Patients will be considered “off treatment” 72 hours following TAE
- Participant requests to be withdrawn from active therapy
- Unacceptable Toxicity as defined in section **3.2.4**
- Investigator discretion

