5.3.1 Investigator Responsibilities

The Investigator will conduct the study in accordance of the investigational plan, any IRB-imposed conditions, and applicable FDA regulations for protecting the rights, safety and welfare of subjects under the investigator's care, and for obtaining informed consent from each research participant prior to any study related procedures. Investigators are also responsible for maintaining control of the investigational device. The Investigator will also assure monitoring is conducted according to the monitoring plan. IRB approval of the study must be obtained prior to study start and this documentation will be on file. The Investigator will promptly notify the IRB of any significant new information about this investigation.

This clinical study is being conducted at Clinical Center National Institutes of Health. Investigators may determine if potential subjects would be interested in taking part in the investigation but written informed consent will not be obtained from study participants and study participation will not be allowed prior to IRB approval.

The investigational device will only be used on research subjects with the investigator's supervision and will not be used on any person who is not authorized under 21CFR812 to receive it.

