5.4 DATA AND SAFETY MONITORING PLAN

5.4.1 Principal Investigator/Research Team

The clinical research team will meet on a routine basis when patients are being actively treated on the trial to discuss each patient. Decisions about ongoing enrollment and intervention will be made based on the toxicity data from prior patients.

All data will be collected in a timely manner and reviewed by the principal investigator or a lead associate investigator. Adverse events will be reported as required above. Any safety concerns, new information that might affect either the ethical and or scientific conduct of the trial, or protocol deviations/reportable events will be immediately reported to the IRB using iRIS.

The principal investigator will review adverse event and response data on each patient to ensure safety and data accuracy. The principal investigator will personally conduct or supervise the investigation and provide appropriate delegation of responsibilities to other members of the research staff.

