5.4.2 Monitoring Plan

Accrual and safety data will be monitored by the principal investigator, who will provide oversight to the conduct of this study. The PI will continuously evaluate implementation of the protocol for any unusual or unpredicted complications that occur and will review the data for accuracy and completeness.

Abbreviated Title: RFA + TACE with RO Beads

Version Date: 04/13/2018

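### Section 3.2.4 is internally inconsistent: it halts only enrollment, so staged and repeat bead sessions in registered patients are not automatically held until the IRB acts

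*Combined protocol and SAP*

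**What the plan says.** Section 3.2.4 (Study Stopping Rules) has two triggers: non-laboratory grade 4 toxicity in three or more patients, or one death from any cause, in each case within 72 hours of TAE. The stated action is "Enrollment will be halted and the IRB notified if" either is met. For patients already in the study it adds "All patients will be monitored until there is improvement or resolution of toxicity". It ends by saying of the IRB that, once its review is complete, "they must give their permission for the study to resume".

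Bead sessions do not end when a patient is enrolled. Section 3.2 leaves retreatment to the physician's recommendation. Section 3.2.1 allows each lobe to be embolized in its own session when disease is multifocal or bilobar. The calendar in section 3.3 lists TAE among the research team's procedures and marks it again in the post-treatment and follow-up columns, the latter running to 12 months from initial treatment.

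Four other sections bear on whether those sessions can be stopped:
- 3.4.1 allows removal from protocol therapy for "Unacceptable Toxicity as defined in section" 3.2.4 and for "Investigator discretion".
- 5.3.1 has the investigator conduct the study "in accordance of the investigational plan, any IRB-imposed conditions, and applicable FDA regulations".
- 5.4.1 states: "Decisions about ongoing enrollment and intervention will be made based on the toxicity data from prior patients".
- 5.4.2 states: "The PI will continuously evaluate implementation of the protocol for any unusual or unpredicted complications that occur".

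**The concern.** A stopping rule should settle in advance what happens after a serious signal, so that nobody has to decide it under pressure. Here the operative words stop one thing, new enrollment, while the title and last sentence read as if everything stops. Staff with a second-lobe session booked for the following week cannot tell from 3.2.4 whether it may go ahead.

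At stake is the interval between a trigger (a death within 72 hours, or the third patient with a qualifying grade 4 event) and the IRB's decision. Read literally, the same intervention may continue in registered patients during that interval unless someone chooses to stop it. The mismatch is greatest after accrual closes: a repeat session can still produce a trigger event, but there is no enrollment left to halt.

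**Working it through.** Section 3.2.4 gives no figure on this point to reproduce, so the check is mainly a comparison of text.

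**1. What is halted.** Section 3.2.4 names enrollment and nothing else. The protocol does not treat enrollment and treatment as one thing: the sentence quoted from 5.4.1 names enrollment and intervention separately.

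**2. What the triggers count.** Both triggers refer to the 72 hours after TAE and are not limited to a patient's first TAE. An event after a staged or repeat session therefore counts. The triggers cover sessions that the action does not reach.

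**3. Which sessions remain open.**
- *Staged and repeat sessions:* allowed by 3.2, 3.2.1 and 3.3, and none is made conditional on 3.2.4. Patients count as off treatment 72 hours after TAE (3.4.1 and the calendar footnote), but the calendar still lists repeat TAE by the study team after that point.
- *First sessions:* section 9.6 places consent at admission for treatment, and section 2.3 requires registration within 24 hours of consent. The gap between registration and first treatment should be short, so few patients would be caught in it.

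**4. Whether another section supplies the hold.**
- 3.4.1, toxicity criterion: acts on an individual patient. It does not hold other patients' sessions.
- 3.4.1, investigator discretion: permits a hold and does not require one.
- 5.3.1: binds the investigator to IRB conditions, but only once the IRB has set them.
- 5.4.1: requires that decisions on intervention be based on toxicity data, but does not fix the decision.
- 5.4.2: requires continuous evaluation by the investigator, with no stated action.

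None imposes an automatic hold in the interval before the IRB acts.

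**5. Calendar bound.** Input: the 3.3 calendar, with TAE possible up to 12 months from initial treatment. The period with no enrollment to halt but TAE still allowed, counted from the last patient's first treatment, equals W months, where W is the time from first treatment to the last further session. The calendar gives W ≤ 12. If further sessions in practice end at W = 2 or 3 (assumptions, not document figures), the period is 2 or 3 months. This is elapsed time, not exposure or risk.

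**6. Time to the IRB.** Section 3.2.4 sets no deadline for notification. Section 5.4.1 has safety concerns reported immediately. Section 5.2.1 allows up to 7 days for reportable deaths and unanticipated problems. A trigger event would plainly be a safety concern, so the immediate report is the relevant standard and 7 days is an outer limit for reports in general. IRB review time is added to this and is not stated.

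**The case against.** The best counter-argument is in 3.2.4 itself. A section titled as study stopping rules, whose last sentence requires permission before the study may resume, presupposes that the study has stopped. On that reading the fault is loose drafting and no safeguard is missing. This stands as evidence of intent. It does not remove the inconsistency with the operative words, and if a full pause was intended, the rewording only says so.

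A second argument is that halting enrollment alone is defensible here. The bead is 510(k)-cleared (section 1.2 and Appendix A), patients are candidates for standard clinical TAE (2.1.1), and section 9.5 expects device risks to match those of the clinically indicated procedure. The triggers apply whatever the cause, so an automatic hold could interrupt a half-finished bilobar treatment because of an unrelated death in another patient. This also stands. It limits the severity and is the reason for a clinical-need exception.

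Three stronger readings are tempting, and the documents do not support them:
- *Treatment would continue without oversight.* The IRB is notified, safety concerns go to it immediately under 5.4.1, and it can impose conditions under 5.3.1.
- *First sessions are a material part of the gap.* Consent at admission for treatment (9.6) makes that unlikely.
- *The 3.4.1 cross-reference should become mandatory removal after one grade 4 event.* Section 3.2.4 triggers at study level but does describe a patient-level event, so 3.4.1 can be applied sensibly. Mandatory removal after a single event of any cause would be a new rule with no justification in the documents.

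**Conclusion.** The point holds as an internal inconsistency in 3.2.4. The operative action is narrower than the section's title and last sentence imply. Staged and repeat LUMI/TAE sessions in registered patients are not automatically held after a trigger, and a hold before the IRB acts depends on discretion under 3.4.1, 5.4.1 and 5.4.2. Once accrual closes, the named action halts nothing.

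The size cannot be stated in sessions or events: the documents give no retreatment rate, no timing of staged sessions, no toxicity or death rates and no IRB review time. The 12-month figure is an upper limit taken from a calendar described as typical. The conclusion rests on giving the word enrollment its ordinary meaning, distinct from treatment, which the wording of 5.4.1 supports.

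This is a minor safety clarification. It does not affect the descriptive primary objective, the sample size or the analysis.

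**What to change.** Reword the opening of 3.2.4 along these lines, keeping the two triggers as they are:

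*Enrollment and further LUMI/TAE sessions under this protocol, including staged and repeat sessions in registered patients, are suspended and the IRB notified if: [existing triggers]. Individual sessions may proceed for documented clinical need with IRB agreement.*

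Leave 3.4.1 unchanged.

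The cost is a short rewording of one section. The downside is that a clinically planned session may be delayed or moved off protocol, since these patients could otherwise receive standard TAE. The clinical-need exception limits this.

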3.3 TYPICAL STUDY CALENDAR*

Procedure	Screening	Pre-operative evaluation prior to receiving LUMI beads treatment	Treatment	Post Treatment	Follow up
		Day 0 to discharge or until off treatment ^b		Within 2 months post treatment	Any time point up to 12 months from initial treatment
Procedures performed by the Referring/ Primary Team					
Evaluation to determine if patient is eligible for TAE	X				
H&P to include baseline symptoms, concomitant medications, etc.	X				
Labs	X				
Procedures performed by the Research Study Team					
Consent	X				
Review of Radiological Assessments ^a	X	X	X	X	X
Review of H&P, labs, and concomitant meds		X			
TAE (if appropriate may include thermal ablation)			X	X ^c	X ^c
Response Evaluation			X	X	X
Adverse Events			X	X ^d	X ^d

^a CT/ CBCT, MRI, or PET scan. All radiological imaging to be performed as clinically indicated and based on the status of the patient.

^b Off treatment is 72 hours post TAE.

^c Patient may require repeat procedures

^d See section 4.1.4 for AE data collection and management during the follow up period.

* Primary teams determine course of follow up, but usually request treating Interventional Radiologist input.

Abbreviated Title: RFA + TACE with RO Beads

Version Date: 04/13/2018

3.4 CRITERIA FOR REMOVAL FROM PROTOCOL THERAPY AND OFF STUDY CRITERIA

3.4.1 Criteria for removal from protocol therapy

- Toxicity that prevents further imaging (e.g., renal dysfunction as serum creatinine >2.0mg/dl and precludes CT or MRI imaging)
- Patients will be considered “off treatment” 72 hours following TAE
- Participant requests to be withdrawn from active therapy
- Unacceptable Toxicity as defined in section **3.2.4**
- Investigator discretion

3.4.2 Off-Study Criteria

- Inability to complete a single session of TAE
- Completed 12-month follow-up period
- Participant requests to be withdrawn from study
- Loss of capacity to provide informed consent
- Death
- Patient becomes eligible for hepatic surgical resection, transplant, or other treatment.

Eligible candidates who have signed the consent and become unable to undergo treatment (due to rapid progression of diseases, etc.) will come off the study. CRO will be notified of the off study reason.

